Neurofeedback Enhanced Cognitive Reappraisal Training

Principal Investigator (PI): [name] [name]

University of Michigan

Dept of Psychiatry

[name]

Email: [contact]

Co-Investigator(s):

[name], [name], [name], [name], [name], [name], [name]

Sponsor:

Brain & Behavior Research Foundation

HUM Number:

HUM00209563

NCT Number:

NCT06132659

Version:

3.21.2025

DETAILED IRB PROTOCOL**1. Objective**

Anxiety disorders are the most common mental health condition worldwide and a leading cause of disability. The development of novel interventions to treat anxiety has lagged the advancements made regarding the neurobiology of emotion and cognitive processes directly related to treatment. This proposal will utilize real-time functional magnetic resonance imaging neurofeedback (NF) to modulate key brain regions involved in emotion regulation to enhance effectiveness of cognitive reappraisal, a central skill taught in evidenced-based psychotherapies. This innovative project will identify 1) the ability of adults with anxiety to self-modulate brain function in regions specific to healthy emotion regulation using NF and 2) the potential impact of neuromodulation on improved emotion regulation ability and anxiety reduction.

2. Specific Aims/Hypotheses

Aim 1A. Evaluate the ability of adults with anxiety to increase prefrontal cortex activity during CR based on NF.

Primary outcome 1A: BOLD activation. Change in PFC activity (baseline to transfer run) from the reappraise > look contrast.

Hypothesis 1A: Participants receiving veritable-NF will show a greater activation increase in the PFC compared to sham-NF.

Aim 1B. Determine the relationship between prefrontal cortex activity recruitment and CR ability in adults with anxiety.

Primary outcome 1B: Negative affect ratings. Decrease in negative affect ratings (baseline to transfer run) from reappraise > look contrast.

Secondary outcome 1B: Prefrontal-amamygdala connectivity. Change in amygdala-PFC functional connectivity (baseline to transfer) from reappraise > look contrast.

Hypothesis 1B1: Participants receiving veritable-NF will show greater CR ability compared to those receiving sham-NF.

Hypothesis 1B2: prefrontal cortex activation will positively correlate with CR ability.

Aim 1C. Assess the impact of NF on anxiety symptoms and CR use over time (exploratory).

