4.3.4 Study Visit 3: fMRI Scan

Study Visit 3 will follow the same procedures as Study Visit 2 of Phases 1 and 2, including pregnancy testing of female participants. However, half of the participants will be randomized to complete the ERT with veritable neurofeedback from the dm/vLPFC, while the other half will be randomized to complete the ERT with sham neurofeedback. Participants in the sham group will complete the same ERT as the veritable NF-group, however, the thermometer will display a pseudo-random feedback signal. This signal is generated to match the spectral characteristics of true feedback (from phases 1 and 2), including the same average success rate to control for the rewarding aspects of receiving feedback.

In the event of unexpected technical difficulties involving the scanner or neurofeedback software, subjects may be invited to complete additional fMRI sessions.

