4.5.2 Scan-Related Measures

Pre-NF interview.

- Belief about brain self-control³⁵
- Motivation⁶⁴
- Expected success to regulate brain during NF and in using CR³⁵

fMRI Scan.

fMRI scanning will occur on a 3.0T GE Discovery MR750 scanner with a 32-channel receiver array head coil and a multi-band slice accelerated echo-planar imaging (EPI) sequence: 2.4mm isotropic resolution, 60 slices; TR/TE 800/30ms, flip angle=52°; multiband factor=6. Whole-brain T1-weighted scans will be acquired with a 3D MPRAGE sequence: 1mm isotropic resolution; TR/TI/TE/FA=2850ms/1060ms/2.3ms/8°; parallel acceleration factor=2. This imaging protocol matches that of the ABCD Protocol, providing high spatial- and temporal-resolution imaging of the functional and structural brain networks and is excellent in signal recovery in areas of high susceptibility artifact.

Emotion Regulation Task - Phase 1. Participants will complete 4-6 runs of the Emotion Regulation Task (ERT), adapted from Keller et al.³⁵. Each run consists of 18 alternating ‘look’ and ‘reappraise’ trials. Each trial will begin with a 1s instruction cue to either ‘look’ or ‘reappraise’, followed by a presentation of a 6-30s negatively-valanced image from the International Affective Picture System⁶⁵ and the Open Affective Standardized Image Set⁶⁶, and a 4-6s fixation screen. At the end of the run participants will rate their negative affect.

Participants in Phase 1 will complete the ERT without neurofeedback to evaluate offline that the task activates areas of interest using traditional fMRI analytical methods. Participants will be recruited in groups of 4-8 to test continued iterations of task parameter modifications (e.g., timing, directions,

number of trials, images) until significant activation is reached in the contrast of interest (reappraise > look) averaged across subjects ($p < 0.05$ small volume corrected for multiple comparisons).

Note: Design parameters are anticipated, as task piloting in Phase 1 may reveal a need to make minor changes. Any such changes will not affect subject risk. Changes that do will be submitted for approval to the IRB.

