Emotion Regulation Task. Half the participants will be randomized to complete the ERT with veritable feedback from the PFC as described in Phase 2. The specific region of interest (dmPFC or vLPFC) will be determined by the results of Phase 2 and arm 1 of Phases 3 and 4. Participants in the sham group will complete the same ERT as the veritable nf-group, however, the thermometer will display a pseudo-random feedback signal. This signal is generated to match the spectral characteristics of true feedback (established from Phase 2), including the same average success rate to control for the rewarding aspects of receiving feedback. As participants are blind to group assignment, inclusion of a sham-group controls for practice effects, fatigue, and learning that may occur without NF. On each trial of the task, a 4s presentation of vLPFC/dmPFC activity (reappraisal trials) or a crosshair (look trials) will appear following the image presentation screen. In the first functional run ('baseline'), participants complete the ERT without NF to establish baseline activity in the two regions of interest (ROIs: vLPFC and dmPFC), based on masks from previous CR meta-analyses (e.g., ^{20,21}). In the middle runs, participants complete the ERT with NF. In the final functional run ('transfer'), participants again complete the ERT without NF to establish ability to implement learning from NF training.

The NF set-up will utilize custom software, developed by co-investigator [name]. This includes motion correction, linear trend removal and spatial smoothing for each image presentation. The BOLD percentage signal change within the ROI is calculated using most recent "reappraise > look" contrast and fed back as a visual display reflecting BOLD signal change. The feedback display shows a thermometer whose minimum is initially set at 0% signal change. Bars fill the thermometer image to correspond to the increase in participant's brain activity using custom MATLAB scripts. On no feedback runs (baseline and transfer), the display shows a crosshair or a static thermometer.

Post-NF interview.

- Difficulty to complete the task
- Comments and suggestions about the task, including appraisals, affect, and arousal ratings of the images
- Perceived control of brain activity and perceived success of CR during NF³⁵
- Tolerability and acceptability of NF
- Manipulation check of group assignment

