4.6 Compensation

It is important that participants feel adequately compensated for the time spent participating in the various components of the study, including completing the diagnostic interview, being scanned, performing the NF task, completing self-report measures, and traveling to the research site.

	Amount
Baseline Assessment:	\$20
Training:	\$20
MRI Scan:	\$50
Follow-Up Assessments:	\$20

Participants who complete the study will be eligible to receive up to \$110.

These values are similar to those used by other fMRI studies at the University of Michigan. If participants withdraw from the study early, they will be paid for the parts of the study they completed. Participants will be paid by check or gift card.

If a participant is asked to return for a second MRI scan brought on by scanner or neurofeedback malfunction, they will be compensated accordingly.

5. Participant Withdrawal

Participants may withdraw from the study at any time for any reason. The reasons a participant may withdraw include, but are not limited to:

- feeling claustrophobic in the MR scanner
- not desiring to continue

Researchers may withdraw a participant from the study if they have a reason to doubt the quality or validity of the data the participant would provide. Reasons may include, but are not limited to:

- participant being unable to hold still in the scanner
- participant no longer meeting criteria
- participant being unable to perform required tasks
- participant not complying with researcher or MRI tech instructions

6. Statistical Design

Aim 1. Evaluate the ability of adults with anxiety to increase prefrontal cortex activity during CR based on NF.

The task will be processed and analyzed using the same methods as Aims 1 and 2. To assess group differences in neuromodulation ability (**hypothesis 1**), a repeated-measures linear mixed effects model (LME) with participant as a random intercept, will examine the 3-way interaction of group (veritable-NF, sham-NF) x condition (reappraise, look) x time (baseline, NF1, NF2, NF3, transfer) on extracted BOLD activation from the dm/vLPFC mask.

Aim 1B. Determine the relationship between prefrontal cortex activity recruitment and CR ability in adults with anxiety.

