To assess group differences in CR ability (**hypothesis 1B1**), a repeated-measures LME with participant as a random intercept, will examine the interaction of group (veritable-NF, sham-NF) x condition time (baseline, NF1, NF2, NF3, transfer) on negative affect ratings and prefrontal-amamygdala connectivity during the ERT. We will use a psychophysiological interaction analysis to measure prefrontal-amamygdala connectivity. Deconvolved time series from anatomical bilateral amygdala seeds for each participant will be multiplied by a vector for the reappraise > look contrast at each run. Regressors for the seed time series, the original condition and the interaction term will be convolved with the canonical hemodynamic response function. Contrast maps will be entered into second-level random effects analyses to test if veritable-NF shows greater prefrontal-amamygdala connectivity than sham-NF.

For hypothesis 1B2, linear regressions will examine run-by-run associations between dm/vlPFC activity and 1) negative affect ratings and 2) prefrontal-amamygdala connectivity, across all participants irrespective of training condition.

Aim 1C. Assess the impact of NF on anxiety symptoms and CR use over time (exploratory).

To examine the effect of NF on anxiety (**hypothesis 1C1**), a repeated-measures LME with participant as a random intercept, will examine the effect of time (baseline, 1 month) x group (veritable-NF, sham-NF) on the HAM-A. To examine the effect of NF on CR use (**hypothesis 1C1**), a repeated-measures LME with participant as a random intercept will examine the interaction of time (baseline, 2-week, 1-month) x group (veritable-NF, sham-NF) on the ERQ.

Linear regressions will examine the association between dm/vlPFC change (transfer-baseline) and change in HAM-A and ERQ scores (1 month – baseline) across all participants (**hypothesis 1C2**). Exploratory: Mediation will test if change in dm/vlPFC activity mediates the relationship between NF group and change in HAM-A or ERQ scores.

7. Data and Safety Monitoring Plan

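### Primary outcome 1B needs negative affect rated separately for look and reappraise, but the only in-scan rating described comes at the end of a mixed run and is not tied to condition

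*Combined protocol and SAP*

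**What the plan says.** Section 2 defines primary outcome 1B as: "Decrease in negative affect ratings (baseline to transfer run) from reappraise > look contrast".

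The in-scan rating appears in Section 4.5.2, in the paragraph on the Phase 1 task. Each run has 18 trials that switch between look and reappraise, and then: "At the end of the run participants will rate their negative affect". A note after this paragraph says: "Design parameters are anticipated, as task piloting in Phase 1 may reveal a need to make minor changes".

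Three other places bear on what happens at the randomised scan.

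- Section 4.3.4 carries the pilot procedures forward: "Study Visit 3 will follow the same procedures as Study Visit 2 of Phases 1 and 2".
- The randomised-task paragraph of Section 4.5.2 says: "Half the participants will be randomized to complete the ERT with veritable feedback from the PFC as described in Phase 2". It adds a 4 s display to each trial and describes no affect rating in the scanner.
- The post-scan interview in Section 4.5.2 includes: "Comments and suggestions about the task, including appraisals, affect, and arousal ratings of the images". The schedule in Section 4.5 also lists image appraisals after neurofeedback.

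In Section 6, the BOLD model lists its condition levels: "condition (reappraise, look) x time (baseline, NF1, NF2, NF3, transfer) on extracted BOLD activation". The affect and connectivity model does not: "x condition time (baseline, NF1, NF2, NF3, transfer) on negative affect ratings and prefrontal-amamygdala connectivity during the ERT".

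**The concern.** A contrast between two conditions needs the outcome recorded under each. One end-of-run rating after a mixed run gives a single figure for the run as a whole. It cannot show whether affect fell because reappraisal improved or because the participant reacted less to every image.

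That distinction is what 1B is meant to capture, and it is the affect part of hypothesis 1B1 on cognitive reappraisal (CR) ability. If the scanner task takes one overall rating, the trial would reach analysis with a primary outcome it cannot compute as defined. The condition term in the affect model would fail for the same reason.

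**Working it through.** The plan gives no figure to reproduce here. The check is whether the described data identify the stated contrast.

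**Inputs**
- Conditions: 2 (look, reappraise), Section 2.
- Runs in the 1B definition: 2 (baseline, transfer), Section 2.
- Runs in the model: 5 (baseline, NF1, NF2, NF3, transfer), Section 6.
- Groups: 2 (veritable, sham), Section 6.
- Ratings per run: not stated. Both one overall rating and one per condition are examined.

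**Values needed and supplied, per participant**

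| | Needed, labelled by condition | One rating per run |
|---|---|---|
| 1B | 2 × 2 = 4 | 2, unlabelled |
| Condition × time model | 2 × 5 = 10 | 5, unlabelled |

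**Estimability.** Let L and R be mean affect under look and reappraise, with B for baseline and T for transfer.

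- 1B = (R_T − L_T) − (R_B − L_B).
- Treat one overall rating as a weighted average: y = (1 − w)L + wR.
- To recover the transfer part of 1B from y_T, some multiplier a must satisfy a·w = 1 and a·(1 − w) = −1.
- Adding the two equations gives a = 0, which contradicts the first. No weight works, and the same holds at baseline.

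A numerical rank check agrees.

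- One rating per run, one participant: rank 5 of 10 run-by-condition means. 1B is not estimable for w = 0.3, 0.5 or 0.9.
- One rating per run, two groups: rank 10 of 20 (2 × 2 × 5). The group difference in 1B is not estimable. The group difference in change of overall affect is.
- One rating per condition per run: rank 10 of 10. 1B is estimable.

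**Illustration (hypothetical scores, w = 0.5).** In each row the overall rating falls from 6 to 5.

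| Baseline look/reappraise | Transfer look/reappraise | 1B |
|---|---|---|
| 6/6 | 5/5 | (5−5) − (6−6) = 0 |
| 6/6 | 6/4 | (4−6) − (6−6) = −2 |
| 6/6 | 4/6 | (6−4) − (6−6) = +2 |

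The same observed ratings fit no effect, improvement or worsening.

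**Other possible sources of condition-level ratings**
- Trial components in Section 4.5.2 are cue, image, fixation and, in the randomised task, the 4 s display. None is a rating.
- The post-scan image ratings are retrospective and are not named as the source of 1B.
- In Section 6 the affect model keeps the word for condition, most likely with a dropped multiplication sign, but does not say where condition-level ratings come from.

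**The case against.** The strongest reply is that the sentence on ratings does not say how many are taken. One look and one reappraise rating at the end of each run fits its wording, and it is the reading that reconciles Sections 2, 4.5.2 and 6. The sentence is also pilot text with provisional parameters, and the Phase 2 task description and the Phase 1 and 2 visit text that the protocol points to are not in the document as supplied. All of this stands. It makes the point conditional but does not remove it: nothing available says affect is rated by condition, and no change to the rating is announced.

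A reader might go further in four ways that the documents do not support.

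- **That 1B certainly cannot be computed.** This requires one rating per run, which the text neither states nor excludes.
- **That condition-level affect could never be recovered.** If image presentation is logged (an assumption), the post-scan image ratings might be mapped to run and condition. They are at best a retrospective fallback.
- **That hypothesis 1B1 fails as a whole.** It is also tested on prefrontal-amygdala connectivity, which Section 6 already builds as a reappraise-versus-look contrast in each run. That part is unaffected.
- **That power is lost.** The issue is identification. The plan gives no sample size or effect size for this comparison from which a power loss could be computed.

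**Conclusion.** The stated measurement and the stated primary outcome do not match as written. On the one-rating reading, the 1B contrast and any condition term for affect in hypothesis 1B1 are not estimable at any sample size. A randomised group × time comparison of overall affect would remain valid, and the connectivity analysis and the run-by-run regression for hypothesis 1B2 could still be run. None of these is the stated affect measure of CR ability.

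On the two-rating reading the effect on the data is zero and only the text needs correcting.

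The conclusion assumes that the end-of-run rating applies at the randomised scan through Section 4.3.4, and that no text outside the supplied document specifies ratings by condition. Confidence is moderate for that reason. It should be settled because 1B is a primary outcome and the remedy is cheap.

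**What to change.** 1. In the randomised-task text of Section 4.5.2, require separate negative affect ratings for look and for reappraise in every run, including baseline and transfer. One item for each at the end of the run is enough. State the scale and timing.
2. Define 1B as (reappraise − look) at transfer minus (reappraise − look) at baseline.
3. In Section 6, write the affect model as group × condition (reappraise, look) × time, and the connectivity model as group × time.
4. If both ratings are already collected, saying so in Sections 4.5.2 and 6 is sufficient.
5. If any randomised participants were scanned with a single rating, they lack the contrast. Report 1B on those with both ratings, and overall affect by group × time for all, labelled as a different measure. The documents do not say whether randomised scanning has begun.

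**Cost.** One or two sentences and perhaps a small change to the task script. Assuming 5 s per rating, a second item adds 5 × 5 = 25 s over five runs. A run lasts 18 × (1 + 6 + 4 + 4) = 270 s to 18 × (1 + 30 + 4 + 6) = 738 s if the 4 s display is added to the fixation, and 18 × 11 = 198 s to 18 × 37 = 666 s if it is not. The extra 5 s is therefore between 5/738 = 0.7% and 5/198 = 2.5% of a run. These timings use the provisional Phase 1 ranges.

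End-of-run ratings are open to recall and demand effects. Rating every trial would reduce the recall problem but takes 18 × 5 = 90 s per run, or 7.5 min over five runs, and changes trial timing.

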4.6 Compensation

It is important that participants feel adequately compensated for the time spent participating in the various components of the study, including completing the diagnostic interview, being scanned, performing the NF task, completing self-report measures, and traveling to the research site.

	Amount
Baseline Assessment:	\$20
Training:	\$20
MRI Scan:	\$50
Follow-Up Assessments:	\$20

Participants who complete the study will be eligible to receive up to \$110.

These values are similar to those used by other fMRI studies at the University of Michigan. If participants withdraw from the study early, they will be paid for the parts of the study they completed. Participants will be paid by check or gift card.

If a participant is asked to return for a second MRI scan brought on by scanner or neurofeedback malfunction, they will be compensated accordingly.

5. Participant Withdrawal

Participants may withdraw from the study at any time for any reason. The reasons a participant may withdraw include, but are not limited to:

- feeling claustrophobic in the MR scanner
- not desiring to continue

Researchers may withdraw a participant from the study if they have a reason to doubt the quality or validity of the data the participant would provide. Reasons may include, but are not limited to:

- participant being unable to hold still in the scanner
- participant no longer meeting criteria
- participant being unable to perform required tasks
- participant not complying with researcher or MRI tech instructions

6. Statistical Design

Aim 1. Evaluate the ability of adults with anxiety to increase prefrontal cortex activity during CR based on NF.

The task will be processed and analyzed using the same methods as Aims 1 and 2. To assess group differences in neuromodulation ability (**hypothesis 1**), a repeated-measures linear mixed effects model (LME) with participant as a random intercept, will examine the 3-way interaction of group (veritable-NF, sham-NF) x condition (reappraise, look) x time (baseline, NF1, NF2, NF3, transfer) on extracted BOLD activation from the dm/vLPFC mask.

Aim 1B. Determine the relationship between prefrontal cortex activity recruitment and CR ability in adults with anxiety.

To assess group differences in CR ability (**hypothesis 1B1**), a repeated-measures LME with participant as a random intercept, will examine the interaction of group (veritable-NF, sham-NF) x condition time (baseline, NF1, NF2, NF3, transfer) on negative affect ratings and prefrontal-amamygdala connectivity during the ERT. We will use a psychophysiological interaction analysis to measure prefrontal-amamygdala connectivity. Deconvolved time series from anatomical bilateral amygdala seeds for each participant will be multiplied by a vector for the reappraise > look contrast at each run. Regressors for the seed time series, the original condition and the interaction term will be convolved with the canonical hemodynamic response function. Contrast maps will be entered into second-level random effects analyses to test if veritable-NF shows greater prefrontal-amamygdala connectivity than sham-NF.

For hypothesis 1B2, linear regressions will examine run-by-run associations between dm/vlPFC activity and 1) negative affect ratings and 2) prefrontal-amamygdala connectivity, across all participants irrespective of training condition.

Aim 1C. Assess the impact of NF on anxiety symptoms and CR use over time (exploratory).

To examine the effect of NF on anxiety (**hypothesis 1C1**), a repeated-measures LME with participant as a random intercept, will examine the effect of time (baseline, 1 month) x group (veritable-NF, sham-NF) on the HAM-A. To examine the effect of NF on CR use (**hypothesis 1C1**), a repeated-measures LME with participant as a random intercept will examine the interaction of time (baseline, 2-week, 1-month) x group (veritable-NF, sham-NF) on the ERQ.

Linear regressions will examine the association between dm/vlPFC change (transfer-baseline) and change in HAM-A and ERQ scores (1 month – baseline) across all participants (**hypothesis 1C2**). Exploratory: Mediation will test if change in dm/vlPFC activity mediates the relationship between NF group and change in HAM-A or ERQ scores.

7. Data and Safety Monitoring Plan

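### Primary outcome 1A is a baseline-to-transfer change, but the only between-arm test Section 6 names for it is a five-run interaction, with no contrast, direction or decision rule tied to transfer

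*Combined protocol and SAP*

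**What the plan says.** Section 2 (Specific Aims/Hypotheses) gives primary outcome 1A as "Change in PFC activity (baseline to transfer run) from the reappraise > look contrast". Hypothesis 1A is directional: "Participants receiving veritable-NF will show a greater activation increase in the PFC compared to sham-NF".

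Section 4.5.2 (Emotion Regulation Task) sets out the run structure. The first run is a baseline without feedback. Then "In the middle runs, participants complete the ERT with NF". In the last run, transfer, "participants again complete the ERT without NF to establish ability to implement learning from NF training". The two runs that define the outcome are both without feedback: "On no feedback runs (baseline and transfer), the display shows a crosshair or a static thermometer".

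Section 6 (Statistical Design), under Aim 1, plans a linear mixed model with a random intercept for participant, which "will examine the 3-way interaction of group (veritable-NF, sham-NF) x condition (reappraise, look) x time (baseline, NF1, NF2, NF3, transfer"). It labels the hypothesis 1 rather than 1A, but the aim is worded the same way, so the match is clear. No contrast, direction, alpha or decision rule follows. Elsewhere in Section 6, the transfer-minus-baseline change appears as a predictor for hypothesis 1C2, pooled over arms. An exploratory mediation under Aim 1C uses change in PFC activity without naming the runs.

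**The concern.** The outcome and the test ask different questions. The outcome asks whether the arms differ in how far the reappraise-minus-look response has moved from baseline once feedback is gone. The interaction asks whether the arm difference varies in any way over five runs. A difference present only while feedback is displayed answers yes to the second question and no to the first.

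That pattern is plausible, because only the veritable arm sees its own signal. If a significant interaction were taken as support for hypothesis 1A, the trial could report success on its first-listed primary outcome with no arm difference at transfer, the run meant to show that learning carries over. A multi-df interaction also gives neither a sign nor a single effect estimate for a directional hypothesis.

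**Working it through.** **Inputs from the plan.** Two arms of about equal size (Section 4.3.2), five runs, two conditions, and a random intercept for participant (Section 6). The plan gives no sample size, effect size, SD, run covariance or alpha for this comparison, so there is no figure of its own to reproduce.

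**Assumptions.** n = 20, 30 or 40 per arm; two-sided alpha 0.05; time as a five-level factor; one value per run and condition; independent run errors. Let δ_r be the arm difference in reappraise minus look at run r, in SDs of that per-run value.

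**Formulas.**
- Residual df: 20n observations − 20 cell means − (2n − 2) participant effects = 9(2n − 2), that is 342, 522 and 702.
- Interaction: noncentral F on 4 and 9(2n − 2) df, with λ = (n/2) Σ(δ_r − mean δ)².
- Baseline-to-transfer contrast: noncentral t, with noncentrality (δ_transfer − δ_baseline)/√(4/n).

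**Arms differ only in NF1–NF3.** δ = (0, d, d, d, 0) has mean 0.6d, so the sum is 2(0.36d²) + 3(0.16d²) = 1.2d². For n = 20 and d = 0.5, λ = 10 × 1.2 × 0.25 = 3.0. The contrast has true value zero and rejects in 5%.

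| d (SD) | λ at n = 20/30/40 | Interaction significant | Interaction significant, contrast not (simulated) |
|---|---|---|---|
| 0.3 | 1.08/1.62/2.16 | 11/14/18% | 9/12/15% |
| 0.5 | 3.0/4.5/6.0 | 24/36/47% | 21/32/43% |
| 0.8 | 7.68/11.52/15.36 | 58/78/90% | 53/73/85% |

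**Direction.** With δ = (0, 0, 0, 0, ±0.8), the sum is 0.8 × 0.64 = 0.512 and λ = 5.12/7.68/10.24. The interaction rejects in 40/58/72%, the same whether transfer favours veritable or sham.

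**Correlated runs (simulated, d = 0.5, n = 20).** If both the reappraise-minus-look values and the run means correlate across runs at 0.3 or 0.5, the interaction rejects in about 21% or 19%. If only the reappraise-minus-look values correlate, it rejects in about 14% or 7%. Allowing a point of simulation error, the range is about 7% to 22%. The random-intercept model's own baseline-to-transfer contrast becomes conservative: with both correlated, it rejects in about 3% or 1.5% when there is no effect. The contrast computed from per-participant values stays near 5%.

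**Time as a linear trend.** The test then has 1 df and a sign, but still does not isolate transfer. It rejects in 5% for the symmetric pattern above. It rejects in 12.5/16.5/20.4% when 0.8 SD is present in NF2–NF3 or NF3 only and transfer is null.

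**Power cost of the contrast.** Take d = 1.26/1.03/0.89, which gives the mixed-model contrast 80% power under independent runs.

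| True pattern at effect d | Interaction | Mixed-model contrast | Unadjusted per-participant contrast |
|---|---|---|---|
| Transfer only, or sustained NF1 to transfer (sum 0.8d²) | 82% | 80% | 78–79% |
| Linear build-up (sum 0.625d²) | 70% | 80% | 78–79% |
| d in NF1–NF3, d/2 at transfer (sum 0.8d²) | 82% | 29% | 28% |

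**The case against.** The strongest reply is that the plan already fixes what is to be estimated. Section 2 gives the two runs, the condition contrast and the direction; Section 6 supplies a model containing that contrast. If baseline is the reference level, the group by condition by transfer coefficient is the contrast itself. This is correct, so it would be wrong to infer that the planned model cannot test outcome 1A. But nothing commits the analyst to that coefficient, and five runs allow several follow-up comparisons to be chosen after the data are seen.

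A reader might also infer that the plan specifies an undirected 4-df test and will credit hypothesis 1A on it. The documents do not say so. Section 6 lists five levels of time and says the interaction will be examined; it states no df and no rule for declaring support. The 4-df reading is the natural one but remains an inference.

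Nor is a five-run analysis foreign to the aim. Aim 1A concerns raising PFC activity with neurofeedback, and hypothesis 1A names no run. A difference during feedback is therefore relevant to the aim. It is still not a measure of the outcome declared primary.

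Finally, the contrast can cost much power when carry-over is partial. That stands and must be disclosed: it is the price of testing transfer, which is the stated outcome.

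**Conclusion.** The point holds in this form: the only between-arm test named for primary outcome 1A does not correspond to that outcome, and Section 6 names no contrast, direction or decision rule to connect them. That the two questions differ needs no numerical assumption. The percentages do: they rest on assumed arm sizes, effects and run covariance, with time as a five-level factor. They show that the gap can be large, and do not predict this trial's result.

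Two further readings go too far. The interaction does not have an inflated type I error; with no arm difference in any run it rejects at its nominal 5% under the assumed model. And the same remedy cannot simply be carried over to outcome 1B. That outcome, "Decrease in negative affect ratings (baseline to transfer run) from reappraise > look contrast", has the same run mismatch, since Section 6 analyses affect ratings over the same five runs. But the only rating schedule described, for Phase 1, is "At the end of the run participants will rate their negative affect". The documents do not settle whether the randomised arms rate affect by condition within each run, so the contrast may not be computable.

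**What to change.** Add to Section 6, before the randomised data are analysed:

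- **Primary test of 1A.** One two-sided 1-df contrast at a stated alpha (0.05 is assumed here): veritable minus sham in [(reappraise − look) at transfer] − [(reappraise − look) at baseline], with a 95% CI. Estimate it from per-participant values, adjusting the transfer value for the baseline value. With equal variances and baseline-transfer correlation ρ, adjustment multiplies the standard error of the simple change by √((1 + ρ)/2), for example √0.75 = 0.87 at ρ = 0.5, and uses one df.
- **Sensitivity analysis.** The same contrast from the random-intercept mixed model. It keeps participants with a missing run, but is conservative if reappraise-minus-look values correlate across runs.
- **Secondary.** The five-run interaction and the feedback-run contrasts, with a statement that they cannot alone support hypothesis 1A.
- **Outcome 1B.** State whether affect is rated by condition in each run. If so, apply the same contrast; if not, restate the outcome so that it can be computed.

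The change needs no new scans or visits. At the effects used above, the unadjusted per-participant contrast loses 3–4 points of power against the interaction for a transfer-only or sustained effect, gains about 8 for a linear build-up, and falls to about 28% against 82% if only half the feedback-run effect carries over. Participants without a usable baseline or transfer run leave the primary analysis.
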